7.1 Investigation of adverse events

1) Purpose

Examine the occurrence of adverse events to examine the safety of the protocol treatment.

2) Analysis items

Name of adverse event, date of onset, worst grade, severity, outcome, and association with protocol treatment.

3) Analysis methods

The frequency of adverse events occurring from the start date of radiotherapy to the end of study is tabulated by adverse event name and worst grade (toxicity) according to CTCAE ver.4.0, and the Clopper & Pearson two-sided 95% confidence interval is calculated. Calculate the frequency and rate of adverse events, the frequency and rate of adverse events by severity, and the frequency and rate of grade 3 or higher adverse events.

A serious adverse event is defined as having occurred if at least one of the following adverse events is observed, and the frequency and proportion of serious adverse events is calculated.

- ① Death during protocol treatment or within 30 days of last protocol treatment.
- ② Death with undeniable causal relationship to protocol treatment after 31 days of last protocol treatment.
- ③ Grade 4 infection with neutropenia.
- ④ Grade 4 non-hematological toxicity (excluding adverse events in the blood/bone marrow).

Prepare a list of adverse event cases.

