The frequency of adverse events occurring from the start date of radiotherapy to the end of study will be tabulated by adverse event name and worst grade according to CTCAE ver.4.0. All adverse events are summarized without regard to causal relationships to the study treatment. A serious adverse event is defined as having occurred if at least one of the following adverse events is observed, and the frequency and proportion of serious adverse events is calculated.

- ① Death during protocol treatment or within 30 days of last protocol treatment.
- ② Death with undeniable causal relationship to protocol treatment after 31 days of last protocol treatment.
- ③ Grade 4 infection with neutropenia.
- ④ Grade 4 non-hematological toxicity (excluding adverse events in the blood/bone marrow).

3) Local control rate

The rate of patients with a best overall response of SD or better confirmed by 180 days, starting from the start date of radiotherapy (Day 1). CT (MRI is also acceptable) and whole-body PET-CT will be used to determine overall response such as complete response (CR), partial response (PR), SD, progressive disease (PD) at each imaging time according to the RECIST Guidelines Version 1.1. If imaging is not available, the patient is considered deficient (NE). CR or PR as the best overall response is defined as two or more consecutive CRs or PRs. If the best overall response does not meet the criteria for CR or PR, and the patient has no PD on the 6th dose of nivolumab and Day 120, the best overall response is considered to be SD. For evaluation, target lesions are tumors that are treated with local radiotherapy. If the lesions cannot be evaluated based on the above criteria, they will not be included in the analysis for best overall response.

4) Immunological parameters

Histological examination

- Analysis of the tumor microenvironment by immunohistochemistry.
 - * Immunohistochemistry will be performed in cases with available biopsy and/or resected surgical specimens.

Peripheral blood test

- Analysis of peripheral blood lymphocyte subset
- Measurement of cytokines in plasma
- Analysis of regulatory T cell and antigen-specific T cell function

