6.1. Response to Adverse Events

If Grade 3 or higher adverse events and other clinically significant adverse events occur in the period from the start date of radiotherapy to the Day180, regardless of whether they are related to the study or not, the attending doctor will immediately take appropriate action against the research subject, including explanation and treatment for it, and record its progress in the medical record and the case report form.

Determination of known/unknown events: Based on the content of the most recent nivolumab drug information, events that can be classified as equivalent in name and severity are considered as known events. Other events are handled as unknown events.

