6.2. Response to the occurrence of serious adverse events

If an adverse event as defined in the preceding paragraph is deemed to be serious, it meets one of the following criteria:

- ① Resulting in Death,
- ② Life-threatening,
- ③ Requiring inpatient hospitalization or prolongation of existing hospitalization for treatment,
- ④ Resulting in permanent or conspicuous disability or dysfunction,
- ⑤ Causing congenital anomalies in offspring.

However, hospital admissions stipulated in the research protocol, hospital admissions solely for the purpose of carrying out a therapy or examination planned before the research (before consent was obtained) and during the study (e.g. planned surgery or examinations), and hospital admissions other than for the purpose of therapy or examinations associated with an adverse event (e.g. medical examination) are not treated as serious. In addition, evaluations related to progression of the primary disease or efficacy of treatment are not handled with adverse events.

Attending doctor manage serious adverse events in accordance with the 'Procedures for handling illnesses, etc.'. In addition, attending doctor report serious adverse events to the Adverse Event Information Desk of Ono Pharmaceutical Industries, Ltd. within 72 hours of receiving the information.

7. Criteria for discontinuation and completion

- 1) In this study, completion of protocol treatment is defined as completion of six doses of nivolumab (anti-PD-1 Ab) followed by 22.5 Gy/5 doses/5 days of radiotherapy. Study completion is also defined as the end of observation at 6 months (Day180) after the start of treatment. Survival will, however, be confirmed at the end of the study period.
- 2) Discontinuation of treatment in individual cases is in accordance with '2.5. Criteria for changes of dosage/use'.
- 3) Discontinuation of the trial is decided by the chief investigator at each institution.
- 4) The principal investigator will monitor opinions and information from the nivolumab manufacturer and distributor, academic information such as papers, and regulatory information from PMDA and other sources, and will always manage the appropriateness of continuing this study.

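### The planned serious adverse event proportion comes from a four-item composite that omits events protocol 6.2 calls serious, and nothing reconciles the two definitions

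*SAP*

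**What the plan says.** Protocol 2.6 (Safety) and SAP 7.1 agree with each other. Both introduce the rule with "A serious adverse event is defined as having occurred if at least one of the following adverse events is observed", list the same four items, and calculate the frequency and proportion of serious adverse events from them. The second item is "Death with undeniable causal relationship to protocol treatment after 31 days of last protocol treatment". The fourth is restricted to toxicity outside the blood and bone marrow. Both sections take adverse events from the start of radiotherapy to the end of study.

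Protocol 6.2 uses the same unqualified term for events that result in death, are life-threatening, require or prolong hospitalization, leave permanent or marked disability, or cause a congenital anomaly. The hospitalization criterion reads "Requiring inpatient hospitalization or prolongation of existing hospitalization for treatment" and carries no grade threshold. These criteria apply to the events of the section before: "If an adverse event as defined in the preceding paragraph is deemed to be serious". That section, 6.1, covers Grade 3 or higher and other clinically significant events occurring "from the start date of radiotherapy to the Day180, regardless of whether they are related to the study or not". Section 6.2 adds that "evaluations related to progression of the primary disease or efficacy of treatment are not handled with adverse events", and it requires serious events to be reported to the manufacturer.

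Two other places use seriousness without defining it. Protocol 8.4 makes the CRF the source for a serious/non-serious item, and SAP 8.8 marks serious events with an asterisk.

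**The concern.** Safety is a named secondary endpoint of a study combining radiotherapy with nivolumab, and the serious adverse event proportion is one of its reported results. Under this plan that proportion has the same name as the events identified and reported under 6.2 but is a different quantity.

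The difference matters most for Grade 3 events that put a patient in hospital. Protocol 2.5 already anticipates Grade 3 or higher diarrhea, colitis and hypersensitivity as reasons to discontinue nivolumab, so such events are foreseeable. A reader who takes the published figure as the share of patients with a serious event would not know that they are left out. The figure also need not agree with the CRF item or with the reports sent to the manufacturer.

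**Working it through.** The plan states no figure to reproduce, so the check sets the two definitions side by side and then measures what can be measured.

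**1. Comparison by type of event**

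| Event | Composite (2.6, SAP 7.1) | Protocol 6.2 |
|---|---|---|
| Fatal adverse event on treatment | Yes | Yes |
| Life-threatening Grade 4 event outside blood/marrow | Yes | Yes |
| Grade 3 event requiring admission | No | Yes |
| Grade 3 event causing lasting disability | No | Yes |
| Life-threatening Grade 4 blood/marrow event, no infection, no counted death | No | Yes |
| Fatal adverse event more than 30 days after last treatment, by Day 180, causality not undeniable | No | Yes |
| Death from progression up to 30 days after last treatment | Yes (no exclusion by cause) | Depends on the progression sentence |
| Treatment-related death after Day 180 | Depends on the meaning of end of study | No (6.1 stops at Day 180) |

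The two definitions overlap on death and on part of the Grade 4 and life-threatening events. Four rows meet 6.2 only on the plain wording. The last two rows cannot be settled from the text.

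**2. Length of the late-death gap**

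Inputs: nivolumab starts on Day 15 to 22, with six doses two weeks apart (protocol 2.1). The composite's 30-day limit is in SAP 7.1 and the Day 180 limit is in protocol 6.1. Dosing without delay is assumed.

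- Last dose = start + 5 × 14 days: 15 + 70 = Day 85, or 22 + 70 = Day 92.
- First day beyond 30 days = last dose + 31: Day 116 or Day 123.
- Days to Day 180 inclusive: 180 − 116 + 1 = 65, or 180 − 123 + 1 = 58.
- If treatment stops after one dose: 15 + 31 = Day 46, giving 135 days; 22 + 31 = Day 53, giving 128 days.

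Dose delays shorten these windows. They measure calendar time during which a death could be classified differently. They say nothing about how many such deaths will occur.

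**3. Effect on the reported proportion**

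Let *b* be the number of patients meeting 6.2 only, *a* the number meeting the composite only, and *n* the number treated. Then

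proportion under 6.2 − proportion under the composite = (*b* − *a*)/*n*.

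With *n* = 40, the planned number and assuming all are treated, one patient is 1/40 = 2.5 points. A patient already counted under both definitions moves nothing.

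Illustration with assumed counts, 95% Clopper-Pearson intervals:

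- Composite, 4 patients: 4/40 = 10.0% (2.8 to 23.7%).
- Adding 4 patients who meet 6.2 only (*b* = 4, *a* = 0): 8/40 = 20.0% (9.1 to 35.6%).

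The documents give no rates from which *a* or *b* could be estimated.

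**The case against.** The best defense is that the two definitions serve different purposes. The composite is printed beside the proportion it feeds, so the analysis itself is not ambiguous, and 6.2 governs handling and reporting and specifies no analysis. A tabulation definition and a reporting definition can coexist. That is right, and it limits the point to a shared label and an omitted count. But the documents never say that this is the intention, and both sections use the term without qualification.

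It can also be said that nothing is lost, because every event is tabulated by name and worst grade, and Grade 3 or higher separately. SAP 7.1 and 8.8 also list severity apart from worst grade, which could be a translated name for the CRF serious/non-serious item. The first part stands, but grade does not show who was admitted or disabled. The second part is possible but cannot be confirmed, and even then the result called the serious adverse event proportion would still be the composite. The definition behind the CRF item may lie in separate procedures that the protocol mentions and that are not available here.

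A reader might infer something stronger: that neither definition contains the other, so the figure could be wrong in either direction. The documents do not establish this. The two candidate examples in the other direction each rest on an open reading:

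- A related death after Day 180 counts in the composite only if end of study means later than Day 180. Protocol 7 sets study completion at Day 180, and the schema ends the trial after the Day 180 assessment, yet survival is confirmed at the end of the study period.
- A death from progression falls outside 6.2 only if the sentence on evaluations of progression is meant to cover deaths.

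If both readings go the other way, and Grade 4 is taken as life-threatening, the composite lies inside 6.2. Nor should the five criteria be read as wholly different from the four items, given the overlap on death and on Grade 4 or life-threatening events.

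**Conclusion.** The point holds as an unreconciled definition of a secondary safety result. Following SAP 7.1 as written, the serious adverse event proportion omits four kinds of event that are serious under protocol 6.2. That finding rests only on the plain wording of the two lists and of 6.1. Whether the proportion also includes deaths that 6.2 would not count remains open.

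The size of the gap cannot be computed. It is 2.5 points per patient meeting one definition only, if 40 are treated. The late-death window is 58 to 65 days after six undelayed doses and 128 to 135 days after one dose. The 4/40 and 8/40 figures are illustrations. The most natural reading of the SAP 8.8 asterisk is that it follows SAP 7.1, which would leave events serious only under 6.2 unmarked, but the SAP does not say so.

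The primary endpoint and the grade-level tables are unaffected. The correction is worth making because a reported result would mislead under its present name.

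**What to change.** Reconcile protocol 2.6 and 6.2 with SAP 7.1 and 8.8:

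- **Rename the composite**, for example *early or treatment-related death or Grade 4 toxicity*, and keep its table.
- **Under the serious adverse event heading in protocol 2.6 and SAP 7.1, write:** *number and proportion of patients in the safety analysis population with at least one event that is serious under protocol 6.2, with the event scope and period of protocol 6.1 and 6.2, and a Clopper-Pearson 95% interval.* Keeping the 6.1 entry rule and Day 180 limit makes this count match the events identified and reported under 6.2. Dropping them would create a third definition.
- **State that the SAP 8.8 asterisk and the CRF serious/non-serious item follow 6.2.**
- **Define end of study** for the adverse event tables, and say for each table whether deaths from progression are counted.

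The cost is a wording change, one extra table, and a check of which definition the sites used for the CRF item. The reported serious adverse event percentage will probably be higher than under the composite. No treatment, schedule or clinical rule changes.

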7.2 Investigation of clinical laboratory values

1) Purpose

Examine the clinical laboratory values to examine the safety of protocol treatment.

5) Analysis population

FAS.

2) **Analysis items**

Vital signs (temperature, pulse, blood pressure).

Subjective and objective findings (PS, fever, nausea, vomiting, diarrhea, decreased appetite).

Hematological examination (white blood cell count, neutrophil ratio, lymphocyte ratio, monocyte ratio, eosinophil ratio, basophil ratio, red blood cell count, hemoglobin concentration, MCV, MCH, MCHC, Ht, platelets).

Blood biochemical tests (total protein, albumin, total bilirubin, direct bilirubin, AST, ALT, γ -GTP, BUN, creatinine, LDH, uric acid, CPK, P, Ca, Na, K, Cl, CRP, blood sugar, rheumatoid factor (RF), anti-nuclear antibodies (ANA), SP-D, KL-6, thyroid-stimulating hormone (TSH), free triiodothyronine (free T3), free thyroxine (free T4), CEA, CA19-9).

3) **Analysis methods**

Prepare transition graphs (per individual and group) of the measured values. Calculate the basic statistics (median and quartiles, or frequency and rate) of the measured values.

Prepare lists of vital signs, subjective and objective findings, hematological examination, and blood biochemistry tests.

8. List of patient data

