3.1. Inclusion criteria

Subjects who meet all of the following criteria are eligible in this study.

- 1) Patients with unresectable advanced or recurrent gastric cancer with intolerance or progression after standard treatment (primary and secondary chemotherapy).
- 2) Patients with more than one measurable lesion and with at least one lesion ≥ 2 cm as defined by the RECIST guidelines edition 1.1 on diagnostic imaging (whole-body contrast-enhanced CT or PET-CT) within 14 days before entry.
- 3) Age ≥ 20 years.
- 4) ECOG performance status (PS): 0–2.
- 5) No contraindication for nivolumab (anti-PD-1 Ab) administration.
- 6) No contraindication for radiotherapy.
- 7) The patient's most recent laboratory tests within 14 days prior to enrollment must meet the following criteria. However, if the clinical examination at the time of enrollment is not included within 7 days prior to the first dose of nivolumab, a repeat examination should be performed within 7 days prior to the first dose of the study drug to reconfirm that the most recent clinical examination prior to the first dose of nivolumab meets the criteria below. In all cases, the laboratory values must not have received a G-CSF product or blood transfusion within 14 days prior to the date of testing.

White blood cell count $\geq 3,000/\mu\text{L}$ and neutrophil count $\geq 1,500/\mu\text{L}$

Hemoglobin $\geq 9.0 \text{ g/dL}$

Platelets $\geq 100,000/\mu\text{L}$

Total bilirubin ≤ 2.0 times the institutional standard upper limit (ISUL)

AST (GOT) and ALT (GPT) ≤ 3.0 times ISUL (in case with liver metastasis, ≤ 5.0 times ISUL).

Serum creatinine ≤ 1.5 times ISUL or creatinine clearance (Ccr) estimate $\geq 60 \text{ mL/min}$.

Ccr is calculated by the Cockcroft-Gault formula:

Male Ccr = $\{(140 - \text{age}) \times \text{weight (kg)}\} / \{72 \times \text{serum creatinine level (mg/dL)}\}$

Female Ccr = $0.85 \times \{(140 - \text{age}) \times \text{weight (kg)}\} / \{72 \times \text{serum creatinine level (mg/dL)}\}$

- 8) Patients expected survival ≥ 3 months.

9) Written informed consent is obtained from the patient prior to study enrollment.

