3.1 Case handling

The principal investigator decides on the handling of cases before the data are fixed, following a review of eligibility and non-compliance with the Study Protocol at the case review meeting.

- 1) All enrolled cases: the population of enrolled patients excluding duplicate enrollments and incorrect enrollments.
- 2) All eligible cases: the population excluding ineligible cases (posterior ineligibility, ineligibility at enrollment, offending enrollment) from all enrolled cases.
- 3) Largest analyzed population (FAS): all eligible patients for whom treatment was administered.
- 4) Safety analysis population: all enrolled cases, those for whom treatment was administered.

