3.2 Analysis population

Efficacy is examined in the FAS and safety is examined in the safety analysis population.

4. Examination of test reliability

1) Purpose

Describe the occurrence of major registration violations, discontinuations, drop-outs, etc. in all enrolled cases, and specify the population to be analyzed.

2) Analysis population

All enrolled cases.

3) Analysis items

- (1) Number of cases belonging to the analyzed population.
- (2) Early discontinued or not.
- (3) Any deviations from the Study Protocol.

4) Method of analysis

- (1) Number of cases in the enrolled, eligible, and largest analyzed cohort are tabulated.
- (2) Cases of early discontinuation are tabulated according to reason and institution.
- (3) Cases of deviation from the Study Protocol are tabulated according to reason and institution.
- (4) A list of cases of treatment failure, early discontinuation, and deviations from the Study Protocol is prepared.

5. Comparability considerations

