5.2 Treatment status

1) Purpose

Assessing treatment status.

2) Analysis population

FAS.

3) Analysis items

- (1) Number of subjects who do not complete radiotherapy or discontinue radiotherapy by Day 14 and the reasons for those discontinuations.
- (2) During protocol treatment (from the start of radiotherapy to the sixth dose of nivolumab), distribution of the number of doses of nivolumab, distribution of the number of days between doses, and reasons for discontinuation of nivolumab.

4) Analysis methods

- (1) Calculate the completion rate of radiotherapy and determine the frequency of uncompleted treatment by reason of incompleteness.
- (2) Calculate the distribution of nivolumab dosing frequency and the proportion of protocol treatment completed. Calculate the basic statistics of the number of days between doses.
- (3) Prepare a list of the above treatments.

6. Efficacy considerations

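### SAP 7.2 summarises laboratory and vital-sign safety in the FAS, although SAP 3.2 and listing 8.9 use the safety analysis population

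*SAP*

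**What the plan says.** SAP 3.1 defines the two populations that matter here. The first is "Safety analysis population: all enrolled cases, those for whom treatment was administered". The second is "Largest analyzed population (FAS): all eligible patients for whom treatment was administered". Eligible cases are in turn "the population excluding ineligible cases (posterior ineligibility, ineligibility at enrollment, offending enrollment) from all enrolled cases". The principal investigator settles the handling of each case after a case review meeting, before the data are fixed.

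SAP 3.2 allocates the populations: "Efficacy is examined in the FAS and safety is examined in the safety analysis population".

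SAP 7.2 is the second part of section 7, on safety. Its purpose is "Examine the clinical laboratory values to examine the safety of protocol treatment", and its population line reads FAS. It asks for individual and group transition graphs, for medians and quartiles or frequencies and rates, and for lists of the measurements. SAP 8.9 asks for lists of the same measurements in the safety analysis population.

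SAP 5.2, under section 5 on comparability, also names the FAS. One of its tasks is "Calculate the completion rate of radiotherapy and determine the frequency of uncompleted treatment by reason of incompleteness". Listing 8.6, on treatment status, uses the safety analysis population. SAP 5.1 reports baseline data in both populations.

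Protocol 3.1, criterion 7, sets laboratory thresholds at enrolment. Where those tests are too old by the first nivolumab dose, it adds that "a repeat examination should be performed within 7 days prior to the first dose of the study drug to reconfirm" that the thresholds are still met. Protocol 2.5 makes failure of the nivolumab start criteria, if treatment cannot resume in the 14 days after the planned date, one reason for discontinuing nivolumab. It lists ineligibility as a separate reason.

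**The concern.** A safety summary should describe everyone who received the treatment, whether or not they later prove to have been eligible. SAP 3.2 adopts that principle and SAP 7.2 departs from it without giving a reason. Two consequences follow. A programmer cannot satisfy 7.2 and 8.9 together, because both ask for lists of the same measurements in different populations. And any treated patient ruled ineligible drops out of the summary statistics and graphs, which are what most readers will look at.

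This matters more than usual because safety is a secondary endpoint of a new combination, and Protocol section 12 itself warns that the combination may increase adverse events. Eligibility is also partly defined by laboratory values, so exclusion from the FAS could be related to the very measurements being summarised.

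**Working it through.** The plan states no figure on this point, so there is none to reproduce. The check compares texts, followed by an illustration of size.

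**Step 1: who is in one set and not the other.** From SAP 3.1, the safety analysis population is enrolled and treated; the FAS is enrolled, treated and eligible. The safety population minus the FAS is therefore exactly the treated patients judged ineligible, including those judged so after enrolment.

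**Step 2: is that group foreseen?** Yes. Protocol 2.5 lists ineligibility, with a known protocol violation or a changed pathology diagnosis as examples, among the reasons for stopping nivolumab and radiotherapy. A patient stopped for that reason has been treated and is ineligible.

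**Step 3: which population each safety output uses.**

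| Output | Population |
|---|---|
| SAP 3.2, general rule for safety | Safety analysis population |
| SAP 7.1, adverse events | None named, so 3.2 applies |
| SAP 7.2, laboratory values, vital signs, symptoms | FAS |
| SAP 8.8, adverse-event listing | Safety analysis population |
| SAP 8.9, listing of the 7.2 measurements | Safety analysis population |
| Protocol 2.10, safety | All enrolled cases |

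Only 7.2 uses the FAS.

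**Step 4: the pre-nivolumab recheck.** Enrolment precedes Day 1 (Protocol 2.9) and nivolumab starts on Days 15 to 22 (Protocol 2.3). The 7-day window before the first dose therefore opens no earlier than Day 15 − 7 = Day 8, so tests done at enrolment cannot fall inside it. The recheck always comes after radiotherapy has begun. It applies the thresholds of an inclusion criterion, so a failure can be read as ineligibility found after treatment started. The same thresholds appear as nivolumab start conditions in Protocol 2.3, and Protocol 2.5 treats failing those as discontinuation. The documents do not say which reading governs the analysis sets.

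**Step 5: size, under assumption.** Suppose N = 40 (the planned number) are treated and k of them are ineligible. Let a eligible and b ineligible patients have a given abnormality. The FAS rate is a/(N − k); the safety-population rate is (a + b)/N. With a = 0 and b = k, and two-sided 95% Clopper-Pearson limits added only to show uncertainty:

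| k | FAS | Upper limit | Safety population | 95% interval |
|---|---|---|---|---|
| 0 | 0/40 = 0% | 8.8% | 0/40 = 0% | 0–8.8% |
| 1 | 0/39 = 0% | 9.0% | 1/40 = 2.5% | 0.1–13.2% |
| 2 | 0/38 = 0% | 9.3% | 2/40 = 5.0% | 0.6–16.9% |
| 4 | 0/36 = 0% | 9.7% | 4/40 = 10.0% | 2.8–23.7% |

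For zero events the upper limit is 1 − 0.025^(1/n); for n = 38 this is 9.3%.

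If four eligible patients also have the abnormality (a = 4, b = k = 4), the FAS gives 4/36 = 11.1% and the safety population 8/40 = 20.0%. If the four excluded patients do not have it (a = 4, b = 0, k = 4), the FAS gives 4/36 = 11.1% and the safety population 4/40 = 10.0%. The direction of the difference therefore depends on who is excluded.

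**The case against.** The best defence is that little is lost. Adverse events fall under SAP 3.2 and are tabulated by worst grade in the safety population, so laboratory worsening recorded as an adverse event is still counted. Listings 8.6, 8.8 and 8.9 cover every treated patient, and listing 8.2 names everyone left out of the FAS with the reason. SAP 7.2 is descriptive: it defines no abnormality endpoint and plans no confidence interval, and removing a few patients from 40 would usually move a median or quartile little. All of this stands and limits the importance of the point. It does not remove the contradiction, and listings do not put patients back into summaries and graphs.

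A reader might infer two stronger things, and the documents support neither.

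- *That SAP 5.2 breaks the same rule and inflates treatment completion.* SAP 3.2 speaks of efficacy and safety only, and 5.2 sits under comparability. Its tension is with listing 8.6, not with 3.2. SAP section 4 already tabulates early discontinuation by reason and institution in all enrolled cases, so non-completion outside the FAS is not hidden.
- *That patients whose blood values worsen after radiotherapy will be removed.* No text calls a failed recheck posterior ineligibility. Under Protocol 2.5 such a patient can be read as discontinued and still eligible, and so remains in the FAS. The case review decides.

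**Conclusion.** The contradiction between SAP 7.2 and both SAP 3.2 and listing 8.9 is plain on the text and needs no assumption. Followed as written, 7.2 omits treated-but-ineligible patients from the laboratory, vital-sign and symptom summaries and from the transition graphs, and from nothing else in the safety reporting.

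The size is unknown because the documents give no count of such patients. The range of 0% shown against 2.5% to 10.0% rests on three assumptions: 40 treated, 1 to 4 of them ineligible, and an abnormality confined to those patients. With no ineligible treated patient the two populations coincide. That failed rechecks would feed this group is a possibility left open by Protocol 2.5 and 3.1 and SAP 3.1, not a stated rule. This is a minor inconsistency in descriptive output, worth correcting because the correction is simple.

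**What to change.** 1. In SAP 7.2, replace FAS with the safety analysis population. This brings it into line with 3.2 and 8.9.
2. In SAP 5.2, report treatment status in the safety analysis population alongside the FAS. This is a consistency improvement that matches listing 8.6 and the practice in SAP 5.1; it does not correct a breach of 3.2.
3. Reconcile Protocol 2.5, Protocol 3.1 (criterion 7) and SAP 3.1, and state before the data are fixed how a failed pre-nivolumab recheck is classified for the analysis sets. This concerns classification for analysis only, not the clinical rule.

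The cost is one changed label in 7.2, one added column in 5.2 and a sentence on classification. No new data are needed. The reported laboratory summaries may look slightly less favourable if ineligible treated patients had abnormal values.
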